#### 6.4.3.10 Breaking time of the tear film

One of the first aspects of the tear film that changes when there is an alteration to the ocular surface, is its stability. In general, if the corneal or conjunctival surface is damaged, it is unlikely that a stable tear film can be maintained.

The most common method to evaluate the stability of the tear film is the evaluation of TRL with fluorescein. Once the fluorescein is instilled, with the cobalt blue filter the patient is asked not to blink. The precorneal colored fluorescein layer will change to less fluorescent or non-fluorescent regions. The time that elapses from the last blink until the appearance of these regions is the TRL. It will be reported in seconds, in the clinical file and in the CRF.

#### 6.4.3.11 Pregnancy test

It refers to the performance of a rapid pregnancy test in all women of childbearing age who wish to enter the study. By fertile age we understand women who have not had their menopause, defined as 12 months since the last menstrual period in women over 40 years of age; or those who underwent bilateral hysterectomy or oophorectomy. Women of childbearing age with contraceptive methods including bilateral tubal obstruction should be tested for pregnancy. This test will be carried out by the IP or the designated team person according to the instructions of the device delivered by the sponsor. When applicable, the completion, result and date must be registered in the CRF. If you do not apply, you must write down the reason

#### 6.4.3.12 Lab tests

The PI will deliver to the subject the order of the studies of BH, QS and PFH, to be carried out in the clinical laboratory designated by the sponsor. The clinical laboratory will deliver to the IP the results for its assessment and registration. The normal parameters to be considered will be the ranges established by the laboratory, nevertheless the clinical criterion of the PI will prevail in the decision of normality or abnormality of the results.

#### 6.4.4 Measurement time

The measurements of the variables of primary and secondary outcome will be made and evaluated for each visit, according to the following:

#### **Scrutiny Visit**

Some of these measurements should be complemented with those of the baseline visit and thus meet the eligibility criteria (see Schedule and study diagram), at the discretion of the PI.

- 1. Signature of informed consent.
- 2. General and ophthalmological clinical history.
- 3. Laboratory sample taking.
- 4. Pregnancy test.
- 5. Review of selection criteria
- 6. Visual ability
- 7. Density of goblet cells (Cytology per impression)
- 8. Intraocular pressure.
- 9. Eye comfort index
- 10. Evaluation of ocular signs and symptoms
- 11. Integrity of ocular surface
- a. Epithelial defects (TF and TVL)
- b. TRL
- 12. Subsequent segment evaluation.
- 13. Vital signs

#### Basal Visit / Day 0.

Some of these measurements will be taken at the screening visit to complete the eligibility criteria (see Schedule and study diagram), at the discretion of the PI, they may be taken to complete the data of the baseline visit.

- 1. Visual ability
- 2. Density of goblet cells (Cytology per impression)
- 3. Intraocular pressure.
- 4. Eye comfort index
- 5. Evaluation of ocular signs and symptoms
- 6. Integrity of ocular surface
  - a. Epithelial defects (TF and TVL)
  - b. TRL
- 7. Subsequent segment evaluation.
- 8. Vital signs
- 9. Evaluation of results of laboratory tests

# Visit 1 / Day 3

It can be done in a period  $\pm 1$  day in relation to day 3 of application.

- 1. Visual ability
- 2. Intraocular pressure.
- 3. Evaluation of ocular signs and symptoms
- 4. Integrity of ocular surface
  - a. Epithelial defects (TF and TVL)
  - b. TRL
- 5. Vital signs
- 6. Delivery of quality questionnaire.
- 7. Evaluation of adverse events.

#### Final Visit / Day 11.

It can be done in a period ± 1 day in relation to the 11th day of the start of application.

- 1. Visual ability
- 2. Density of goblet cells (Cytology per impression)
- 3. Intraocular pressure.
- 4. Eye comfort index
- 5. Evaluation of ocular signs and symptoms
- 6. Integrity of ocular surface
  - a. Epithelial defects (TF and TVL)
  - b. TRL
- 7. Subsequent segment evaluation.
- 8. Vital signs
- 9. Return and evaluation of quality questionnaire.
- 10. Evaluation of adverse events

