# Test product, dose and route of administration, lot number:

- PRO-167. Dexpanthenol 5%. Ophthalmic gel produced by Sophia Laboratories A.S. of V.C., Zapopan, Jalisco, Mexico.
  - Dose: a strip approximately 1 cm long, 4 times a day during the period of vigil, in the bottom of the right eye sac.

Version: 1.0

- Route of administration: ophtalmic.

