#### **Duration of treatment**: 10 days

#### Reference product, dose and route of administration, lot:

- Corneregel®. Dexpanthenol 5%. Ophthalmic gel developed by Bausch & Lomb, Berlin, Germany.
  - Dose: a strip approximately 1 cm long, 4 times a day during the period of vigil, in the bottom of the right eye sac.
  - Route of administration: ophthalmic

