#### 6.3.4.3 Return

The research subjects will return to the staff indicated by the IP in the center their treatments in visits 1 and final. The refund will be made by the research center when the sponsor indicates it. Prior to the return the research center must make a count of the assigned medication and the remaining medication, with the aim of creating an inventory which serves for the final filling of the return form of the medication.

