#### 6.5.1.2 Basal visit

- Review of laboratory tests: refers to the review and analysis by the IP of the results of the BH, QS and PFH. See 6.4.3.12 Laboratory tests.
- Eligibility criteria: with the laboratory results, the subject's profile will be finalized for inclusion or not.
- Assignment: It refers to determining the intervention that the patient will follow during the study. It will be done according to section 7. Methods. Assignment of the intervention. This assignment will be made at the baseline visit (day 0) and will go along with the indication to start the treatment period the next day (day 1).
- Delivery of intervention: Refers to the delivery of the product under investigation to the patient of the study, by the research center. It will be done according to sections 6.3.1 Managed treatments and 6.3.4.1 Delivery and reception.
- Evaluation of variables: The data of the evaluation of the variables listed below can be taken from the scrutiny visit, as long as it does not exceed 7 days prior to this visit. It is the IP's prerogative to decide whether to use the information from the screening visit or to repeat the evaluations on this visit.
  - o Intraocular pressure
  - o Visual capacity
  - o TRL
  - o Epithelial defects (TF and TVL)
  - o Eye signs and symptoms
  - o Subsequent segment
  - o vital signs

- Eye comfort index: see 6.4.3.3 Eye comfort index
- Density of goblet cells (cytology per impression): see 6.4.3.2 Density of goblet cells (cytology per impression)
- Delivery of the subject's diary: It refers to the delivery by the IP to the subject, the subject's daily instrument.
- Delivery of quality questionnaire: It refers to the delivery by the IP to the subject, the quality questionnaire instrument.

#### 6.5.1.3 Visit 1

- Intervention delivery: see 6.5.1.2 Baseline visit
- Return of intervention: refers to the return of research products to the center by the research subject.
- Evaluation of adherence: refers to the assessment made by the IP according to section 6.3.2.1 Procedure to monitor adherence
- Adverse events: see 6.4.3.5 Presence of adverse events
- Intraocular pressure: see 6.4.3.6 Intraocular pressure
- Visual ability: see 6.4.3.1 Visual capacity
- TRL: see 6.4.3.10 Rupture time of the tear film
- Epithelial defects (TF and TVL): see 6.4.3.4.1 Stains
- Eye signs and symptoms: see 6.4.3.4 Eye surface integrity: and 6.4.3.9 Ocular symptomatology

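### The final-visit window (days 10 to 12) opens on the last day of the stated 10-day treatment, so the end-of-treatment measurement has no consistent relation to the last application

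*Combined protocol and SAP*

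**What the plan says.** - **Length and start of treatment.** Section 1 (Summary) states "Duration of treatment: 10 days". Section 6.5.1.2 has the subject "start the treatment period the next day (day 1"), with the baseline visit as day 0. The gel is applied "4 times a day during the period of vigil" (section 1, repeated for both products in sections 6.3.1.1 and 6.3.1.2).
- **Final visit.** Section 6.4.4, Final Visit / Day 11: "It can be done in a period ± 1 day in relation to the 11th day of the start of application". The schedule in section 6.5 gives the same visit as day 11 ± 1, counted from a day-0 baseline.
- **Return of the gel.** Section 6.3.4.3: "The research subjects will return to the staff indicated by the IP in the center their treatments in visits 1 and final". Section 6.3.4.1 and the schedule hand out gel only at baseline and visit 1, so none is left after the final visit.
- **What is measured there.** Goblet cell density (primary for safety, section 6.4.1.1) and the eye comfort index (primary for tolerability, section 6.4.1.2) are measured after baseline only at this visit. Staining and symptoms have their last assessment there.

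The plan does not tie the visit to the last application. It does not cover day-10 applications still due when the tube comes back, and it makes no allowance in the analysis for time since the last application.

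**The concern.** The nominal day 11 fits the stated course: it is the first day after 10 treatment days. The problem lies at the edges of the window. At the early edge, the tube can be taken back on a day when applications are still due, so the schedule itself may shorten the course that the protocol defines. At the late edge, a subject may be examined after a whole day without gel.

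The two primary variables with a single post-baseline reading could therefore be taken on treatment in one subject and off treatment in another, with no second reading to fall back on. Section 8.3.1 declares the product safe and tolerable when no clinical and statistical differences appear in the primary variables. Under such a rule, avoidable variability makes a real difference harder to see. Each group has 12 subjects, so chance imbalance in visit day is possible.

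**Working it through.** **Inputs.** Duration 10 days (section 1); first application on day 1 (section 6.5.1.2); 4 applications a day (section 6.3.1); final visit day 11 ± 1 (sections 6.4.4 and 6.5); comfort index questions about the past week (annex 13.1). The documents give no clock times. I assume a last application between 20:00 and 22:00 and visits between 08:00 and 18:00.

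**The plan's own figure.** Last treatment day = 1 + 10 − 1 = day 10. The first day after treatment is day 11, which reproduces the nominal visit day. The window is 11 − 1 to 11 + 1, that is days 10 to 12. Planned applications = 10 × 4 = 40.

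**Alternative reading.** Counting 11 elapsed days from the day-1 application would give days 11 to 13. This conflicts with the schedule, where baseline is day 0 and the visit is day 11 ± 1.

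**Applications made by a perfect user at a day-10 visit.** 9 × 4 = 36 by the end of day 9, plus 0 to 4 on day 10, giving 36 to 40 (90% to 100%). On the assumed clock times the fourth application always falls after the visit. The documents do not exclude a visit that follows it, so 40 remains possible.

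**Hours since the last planned application** = 24 × (visit day − 10) + visit hour − application hour:
- day 10: 8 − 22 = −14 to 18 − 20 = −2, so the last planned application is still 2 to 14 hours ahead;
- day 11: 24 − 14 = 10 to 24 − 2 = 22 hours;
- day 12: 48 − 14 = 34 to 48 − 2 = 46 hours (1.4 to 1.9 days), with day 11 wholly gel-free.

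**Treated days in the 7-day recall**, excluding or including the visit day:

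| Visit | Recall days | Treated days of 7 |
|---|---|---|
| Day 10 | 3–9 or 4–10 | 7 |
| Day 11 | 4–10 or 5–11 | 7 or 6 |
| Day 12 | 5–11 or 6–12 | 6 or 5 |

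**Adherence.** Section 6.3.2.1 divides by the applications indicated and averages the visits. It does not say whether the denominator shrinks for an early in-window visit. If it does not, and 4 applications are cut off:
- pooled over the course: 36/40 = 90%;
- averaged over visits, with visit 1 after 12 applications: 24/28 = 85.7%, and (100 + 85.7)/2 = 92.9%;
- with visit 1 anywhere in its own window (days 2 to 4, so after 4 to 16 applications): from (100 + 32/36 × 100)/2 = 94.4% down to (100 + 20/24 × 100)/2 = 91.7%.

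All of these lie far above the elimination limit (below 50%, section 6.2.3) and the analysis limit (above 60%, section 8.3.1).

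**The case against.** The strongest reply is that this is an ordinary ±1-day allowance around a correctly placed visit, with little consequence. Much of that stands.

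- A reader might infer that treatment cannot be completed if the visit is on day 10. That goes too far: a visit after the fourth application completes all 40.
- A reader might infer that recovery off the gel hides irritation in subjects seen late. The documents do not support this. Burning, foreign body sensation and itching are asked about for the whole interval since the previous visit and are also marked in the diary after each application (section 6.4.3.9). Staining is also read at visit 1, and adverse events are collected at visit 1, the final visit and the safety call. That leaves goblet cell density, the final staining reading and, to a small extent, the comfort index. The documents give no data on how these change over one or two days.
- A reader might infer bias between the products. Both arms share the window, and allocation is randomised and blinded.
- The lost exposure is at most 10% of applications, and section 8.3.1 regards about 1 cm a day as enough for the study's objective.
- The diary already registers each application, so a new field partly duplicates it. The documents do not say whether the diary records clock time.

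These replies limit the size of the point. They do not reconcile a stated 10-day course with a visit that may take the tube back before the last day's applications are made.

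**Conclusion.** The point holds as a small internal conflict between the stated duration, the return of the tube and the visit window. The window permits anything from up to 4 of 40 applications forgone to one full gel-free day before measurement; it does not make that mixture certain. The application counts and recall days follow from the documents. The 1.4 to 1.9 days rests on the assumed clock times, and the adherence shortfall rests on an unreduced denominator.

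The expected consequence is modest extra variability and an inconsistent meaning of end of treatment, in both arms alike. The amount of variability cannot be computed from the documents. No directional effect is shown, and only a subject already close to an adherence limit could be moved across it. The point is worth correcting because the correction is cheap and because two primary variables have no other post-baseline reading.

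**What to change.** 1. Reconcile the duration in section 1, the start in section 6.5.1.2, the return in section 6.3.4.3 and the window in sections 6.4.4 and 6.5, so that an in-window visit does not cut off the stated course. A window that does not open before the stated duration ends is one way; the choice is the sponsor's.
2. Record the date and time of the last application in the CRF at the final visit. A later opening alone would still leave day-12 visits; this field allows time since the last application to be described or examined.
3. In both adherence formulas of section 6.3.2.1, define the applications indicated as those due before the tube was returned.

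The cost is one line of protocol text, one CRF field and up to one day less scheduling freedom.

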#### Security call / Day 13.

It can be done in a period  $\pm 1$  day in relation to the 13th day of the start of application.

- 1. Ask about the presence of an adverse event.
- 2. Evaluation of results of laboratory test

## 6.5 Timeline and study diagram

Procedures	scrutiny	Basal visit	Visit 1	Final visit	Call Security
Procedures		Day 0	Day 3 ± 1	Day 11 ± 1	Day 13 ± 1
CI signature	Х				
clinic history	Χ				
Ophthalmological clinical history	Х				
Laboratory sample taking	Χ			Χ	
Laboratory tests review		Х			Х
Pregnancy test	Χ			Χ	
Eligibility criteria	Х	Xa			
Assignment		Χ			
Delivery of intervention		Х	Х		
Return of intervention			Χ	Χ	
Adherence evaluation			Х	Х	
Adverse events			Х	Χ	Χ
Intraocular pressure	Х	X 	Х	Х	
Visual ability	Χ	X 	Χ	Χ	
TRL	Х	X 	Х	Х	
Epithelial defects (TF and TVL)	Χ	X 	Х	Χ	
Eye signs and symptoms	Х	X 	Х	Х	
Posterior Segment	Χ	X 		Χ	
Vital signs	Х	X 	Х	Х	
Ocular Comfort Index		Х		Х	
Goblet cell density (cytology by impression)		Х		Х	
Daily delivery of the subject		Χ	Х		
Return / Evaluation of the subject's Journal			Х	Х	
Delivery Quality Questionnaire		Χ			
Return and Evaluation of the quality questionnaire				Х	
Continuity evaluation of the subject		Х	X	X	

a The eligibility criteria will be completed with the revision of the laboratory exams. 1 These measurements may be taken from the result of the screening visit, if it does not exceed the previous 7 days. It is the prerogative of the PI to decide whether to repeat the measurements at the baseline visit.

#### 6.5.1 Procedures to be performed per visit

#### 6.5.1.1 Scrutiny visit

- Signature of informed consent: refers to the signing of the written informed consent document. See 10.3 Consent
- General and ophthalmological clinical history: refers to the technical, clinical and legal document in which the patient's health conditions, medical acts and other procedures performed on the patient are recorded chronologically. It includes the anamnesis and comprehensive ophthalmological exploration that allows to discern the patient's eligibility. If the patient is taken from the established consultation of the study center, he / she will be able to use the existing clinical history, only having to perform an update.
- Taking laboratory samples: see 6.4.3.12 Laboratory tests.
- Pregnancy test: see 6.4.3.11 Pregnancy test.
- Eligibility criteria: refers to the review by the IP, where it states that the subject can be included in the study by meeting the inclusion criteria and not meeting the exclusion criteria. See 6.2 Eligibility criteria
- Intraocular pressure: see 6.4.3.6 Intraocular pressure
- Visual ability: see 6.4.3.1 Visual capacity
- TRL: see 6.4.3.10 Rupture time of the tear film
- Epithelial defects (TVL and TF): see 6.4.3.4.1 Stains
- Eye signs and symptoms: see 6.4.3.4 Eye surface integrity: and 6.4.3.9 Ocular symptomatology
- Posterior segment: see 6.4.3.7 Posterior segment
- Vital signs: see 6.4.3.8 Vital signs

#### 6.5.1.2 Basal visit

- Review of laboratory tests: refers to the review and analysis by the IP of the results of the BH, QS and PFH. See 6.4.3.12 Laboratory tests.
- Eligibility criteria: with the laboratory results, the subject's profile will be finalized for inclusion or not.
- Assignment: It refers to determining the intervention that the patient will follow during the study. It will be done according to section 7. Methods. Assignment of the intervention. This assignment will be made at the baseline visit (day 0) and will go along with the indication to start the treatment period the next day (day 1).
- Delivery of intervention: Refers to the delivery of the product under investigation to the patient of the study, by the research center. It will be done according to sections 6.3.1 Managed treatments and 6.3.4.1 Delivery and reception.
- Evaluation of variables: The data of the evaluation of the variables listed below can be taken from the scrutiny visit, as long as it does not exceed 7 days prior to this visit. It is the IP's prerogative to decide whether to use the information from the screening visit or to repeat the evaluations on this visit.
  - o Intraocular pressure
  - o Visual capacity
  - o TRL
  - o Epithelial defects (TF and TVL)
  - o Eye signs and symptoms
  - o Subsequent segment
  - o vital signs

- Eye comfort index: see 6.4.3.3 Eye comfort index
- Density of goblet cells (cytology per impression): see 6.4.3.2 Density of goblet cells (cytology per impression)
- Delivery of the subject's diary: It refers to the delivery by the IP to the subject, the subject's daily instrument.
- Delivery of quality questionnaire: It refers to the delivery by the IP to the subject, the quality questionnaire instrument.

#### 6.5.1.3 Visit 1

- Intervention delivery: see 6.5.1.2 Baseline visit
- Return of intervention: refers to the return of research products to the center by the research subject.
- Evaluation of adherence: refers to the assessment made by the IP according to section 6.3.2.1 Procedure to monitor adherence
- Adverse events: see 6.4.3.5 Presence of adverse events
- Intraocular pressure: see 6.4.3.6 Intraocular pressure
- Visual ability: see 6.4.3.1 Visual capacity
- TRL: see 6.4.3.10 Rupture time of the tear film
- Epithelial defects (TF and TVL): see 6.4.3.4.1 Stains
- Eye signs and symptoms: see 6.4.3.4 Eye surface integrity: and 6.4.3.9 Ocular symptomatology
- Vital signs: see 6.4.3.8 Vital signs
- Submission of the subject's diary: see 6.5.1.2 Baseline visit
- Return / daily evaluation of the subject: refers to the delivery of the subject's diary to the IP by the subject. The IP will review the diary to assess its correct filler, evaluate the post-application symptomatology and the registration of the applications.
- Continuity assessment of the subject: refers to the determination by the PI and desire of the subject to continue with their participation in the study.

#### 6.5.1.4 Final visit

- Laboratory sample taking: see 6.4.3.12 Laboratory tests
- Pregnancy test: see 6.4.3.11 Pregnancy test
- Return of intervention: see 6.5.1.3 Visit 1.
- Adherence evaluation: see 6.5.1.3 Visit 1
- Adverse events: see 6.4.3.5 Presence of adverse events
- Intraocular pressure: see 6.4.3.6 Intraocular pressure
- Visual ability: see 6.4.3.1 Visual capacity
- TRL: see 6.4.3.10 Rupture time of the tear film
- Epithelial defects (TF and TVL): see 6.4.3.4.1 Stains
- Eye signs and symptoms: see 6.4.3.4 Eye surface integrity: and 6.4.3.9 Ocular symptomatology
- Subsequent segment: see 6.4.3.7 Subsequent segment
- Vital signs: see 6.4.3.8 Vital signs
- Eye comfort index: see 6.4.3.3 Eye comfort index
- Density of goblet cells (cytology per impression): see 6.4.3.2 Goblet cell density (Cytology per impression)
- Return / daily evaluation of the subject: see 6.5.1.3 Visit 1.

• Return / evaluation of the quality questionnaire: refers to the delivery of the quality questionnaire to the IP by the subject.

#### 6.5.1.5 Security call

- Adverse events: see 6.4.3.5 Presence of adverse events
- Review of laboratory tests: see 6.5.1.2 Baseline visit

#### 6.5.2 Diagram of the study

An enrollment time of 30 days is estimated for the total sample.

In order to increase the safety of the participants with the use of the products under investigation, a partial analysis will be carried out following a modification to the Fibonacci method. This methodology will consist of including 33% of the total sample size (4 subjects per group, n = 8), which will complete all the visits and procedures described. Once this group of 8 subjects has finished their participation in the clinical study, a blinded analysis will be carried out. During the period in which this sub-analysis is carried out, the inclusion of new participants will be restricted. Inclusion will resume when the sponsor notifies the research center.

In addition to safety, therapeutic adherence will be evaluated and problems related to procedures will be resolved, should they arise.

[figure not shown]

Figure 1. Diagram of the study

